#### 11.1.2 Criteria for Dose Interruption During a Cycle/Visit

TAK-228 should be withheld for treatment-related toxicities that are grade 3 or higher despite supportive treatment per standard clinical practice. If the event resolves to grade 1 (or grade 2 for hyperglycemia or rash) or to baseline values within 3 weeks of interrupting treatment, then the patient may resume study treatment at a dose level reduced by 1 level.

The following non-hematologic toxicities attributed to TAK-228 would not require dose interruption:

- Grade 3 or higher nausea and/or emesis in the absence of optimal antiemetic prophylaxis (optimal antiemetic prophylaxis is defined as an antiemetic regimen that employs both a serotonin type 3 receptor antagonist and a corticosteroid given in standard doses and according to standard schedules)
- Grade 3 or higher diarrhea that occurs in the absence of optimal supportive therapy
- Grade 3 fatigue

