**TABLE 7 TAK-228 DOSE MODIFICATIONS**

Dose Level	TAK-228 Dose	TAK-228 Number of Capsules and Strength
0	30 mg p.o. QW	Six 5 mg capsules
-1	20 mg p.o. QW	Four 5 mg capsules
-2	15 mg p.o. QW	Three 5 mg capsules
-3	10 mg p.o. QW	Two 5 mg capsules

For patients who are unable to tolerate the protocol-specified dosing schedule, dose reductions or interruptions are permitted to manage drug-related toxicities. Patients whose treatment is interrupted or permanently discontinued due to an AE including abnormal laboratory value must be followed at least once a week for 4 weeks and subsequently at 4-week intervals until resolution or stabilization of the event, whichever comes first. Dose interruptions should be reported on the appropriate Dosage Administration case report form (CRF). The maximum time allowed for toxicity-related treatment interruption is 21 days (3 weeks) from the intended dosing day. If treatment interruption is >3 weeks or more than 3 dose reductions are required, the patient must be discontinued from the study treatment. However, they will need to complete the EOT visit within 30 to 40 days after the last dose of TAK-228, and the patient will continue to be followed for toxicity.

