## **11.3 Excluded Concomitant Medications and Procedures and Potential DDIs**

The following medications and procedures are prohibited during the study:

- Other investigational agents including mTOR, PI3K, and AKT inhibitors
- Other anticancer therapies including chemotherapy, immunotherapy, radioimmunotherapy, targeted agents, radiation, and surgery (palliative radiation and surgery for preexisting lesions is allowed during the study)
- Systemic corticosteroids (either IV or oral steroids, excluding inhalers), unless necessary for the treatment of TAK-228-related rash.
- Antiepileptic drugs for patients with treated brain metastasis
- Concomitant administration of any PPI (e.g., omeprazole, esomeprazole, pantoprazole, lansoprazole, and rabeprazole) is not permitted during the study. Patients receiving PPI therapy before enrollment must stop using the PPI for 7 days before their first dose of study drugs.

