#### 11.6.5 Management of Nausea/Vomiting

Guidance on TAK-228 dose modification for patients with nausea and/or vomiting is provided in Table 12.

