**TABLE 12 MANAGEMENT OF NAUSEA/VOMITING**

Grade	Description	Treatment	Dose Modification
≤2	Loss of appetite with or without decreased oral intake. 1 to 5 episodes of vomiting within 24 hours.	
 
Maximize anti-emetic therapy.
 
Consider IV fluid hydration.
 
	None
≥3	Inadequate oral intake. ≥6 episodes of vomiting within 24 hours.	
 
Maximize anti-emetic therapy.
 
Initiate tube feeding, IVF or TPN.
 
	If experienced for ≤72 hours, hold TAK-228 until ≤grade 1, then resume TAK-228 without dose modification. If experienced for >72 hours despite optimal therapy, hold TAK-228 until ≤grade 1, then resume treatment with the dose of TAK-228 reduced by 1 level.

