**Prevention/Prophylaxis:**

Prophylactic use of antiemetic, antinausea, and antidiarrheal medications are encouraged and may be used before each TAK-228 dosing as needed throughout the study.

IV=intravenous; IVF=intravenous fluids; TPN=total parenteral nutrition.

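### The nausea/emesis waiver in Section 11.1.2 turns on a corticosteroid regimen that Section 11.3 prohibits, so it reaches almost every severe event for which Table 12 directs a hold

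*Combined protocol and SAP*

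**What the plan says.** Four places in the protocol bear on severe nausea and vomiting.

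- **Section 11.1.2** first says to withhold TAK-228 for treatment-related toxicity of grade 3 or higher. It then lists exceptions: "The following non-hematologic toxicities attributed to TAK-228 would not require dose interruption". One exception is grade ≥3 nausea or emesis when optimal antiemetic prophylaxis was absent. That prophylaxis is defined as a regimen that "employs both a serotonin type 3 receptor antagonist and a corticosteroid given in standard doses". Both components are required.
- **Section 11.3** lists among prohibited medications: "Systemic corticosteroids (either IV or oral steroids, excluding inhalers), unless necessary for the treatment of TAK-228-related rash". Section 11.4 (permitted medications) restores no antiemetic use of steroids.
- **Section 11.6.5** refers the reader to a table: "Guidance on TAK-228 dose modification for patients with nausea and/or vomiting is provided in Table 12". For grade ≥3 events lasting up to 72 hours, Table 12 says "hold TAK-228 until ≤grade 1, then resume TAK-228 without dose modification". For events lasting longer despite *optimal therapy*, a term the table does not define, it again directs a hold to grade 1 or lower and "then resume treatment with the dose of TAK-228 reduced by 1 level".
- **The prophylaxis note under Table 12** reads: "Prophylactic use of antiemetic, antinausea, and antidiarrheal medications are encouraged and may be used before each TAK-228 dosing as needed". It names no regimen and makes no exception to 11.3.

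**The concern.** The waiver looks intended for patients whose prophylaxis was inadequate: improve the prophylaxis first, and do not interrupt the study drug for an avoidable event. Because adequate prophylaxis is defined by a drug class that another section forbids, the waiver also reaches patients who had the best prophylaxis the protocol allows. A narrow exception becomes the usual rule, and it sits beside a table that gives a different instruction for the same event.

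At stake is consistent handling of a safety event. Section 3.2 lists nausea and vomiting among the most common treatment-emergent events with TAK-228, without giving grades. Two investigators could treat the same patient differently, and each could cite the protocol. Section 13.1.8 reports the frequency of interruptions and reductions, so those counts would partly reflect which rule each investigator followed.

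**Working it through.** The plan states no figure to reproduce. The main check is a comparison of texts; the arithmetic that follows is conditional.

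**Step 1. Can a compliant patient receive the defined prophylaxis?** Section 11.1.2 requires a corticosteroid at standard antiemetic dose and schedule, which is a systemic (IV or oral) drug. Section 11.3 bars that route, with exceptions for inhalers and TAK-228-related rash only. So the answer is no, apart from a patient who happens to be on steroids for rash.

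**Step 2. How far does the waiver reach?** Its condition, absence of the defined prophylaxis, is met for essentially every grade ≥3 nausea or emesis event.

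**Step 3. Compare with Table 12.**

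| Event (grade ≥3) | Section 11.1.2 as written | Table 12 |
|---|---|---|
| Up to 72 hours | Interruption not required | Hold, then same dose; no prophylaxis condition |
| Over 72 hours, *optimal therapy* given | Interruption not required; silent on dose level | Hold, then one level lower |
| Over 72 hours, *optimal therapy* not given | Interruption not required; silent on dose level | No branch |

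**Step 4. What does *optimal therapy* in Table 12 mean?** There are two readings.

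- *Best therapy that 11.3 permits.* The reduction branch can be reached. Table 12 then gives 20 mg as the next dose, against 30 mg for a patient who is never interrupted.
- *The 11.1.2 regimen.* A compliant patient cannot reach the reduction branch, so events over 72 hours have no Table 12 rule and there is no 30-versus-20 mg conflict.

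**Step 5. Size under the first reading only.** Table 7 gives level 0 as 30 mg and level −1 as 20 mg: (30 − 20)/30 = 33%. The planned total is 16 × 30 = 480 mg. Assume one reduction and no re-escalation (the protocol describes none), with the event after dose *k* and *h* held doses. The loss against taking every dose at 30 mg is

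30*h* + 10(16 − *k* − *h*) mg.

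Table 7's text limits *h*: "The maximum time allowed for toxicity-related treatment interruption is 21 days (3 weeks) from the intended dosing day". With weekly dosing, *h* is at most 3.

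| Event after dose | No dose held | Most doses held |
|---|---|---|
| 1 | 10 × 15 = 150 mg (31%) | *h* = 3: 90 + 10 × 12 = 210 mg (44%) |
| 8 | 10 × 8 = 80 mg (17%) | *h* = 3: 90 + 10 × 5 = 140 mg (29%) |
| 15 | 10 × 1 = 10 mg (2%) | *h* = 1: 30 + 0 = 30 mg (6%) |

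After dose 15 only one dose remains, so *h* cannot exceed 1.

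**Step 6. Events up to 72 hours.** The dose level is the same under both rules. The loss is 30*h*: 0 mg if recovery comes before the next weekly dose, or 30 mg (30/480 = 6%) if one dosing day is missed.

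**The case against.** The strongest reply is that no two instructions are incompatible. Section 11.1.2 removes a requirement to interrupt; it does not forbid interruption, so an investigator who follows Table 12 breaches nothing. Section 11.6.5 sends nausea and vomiting to Table 12, Section 11.1.1 makes grade ≥3 related events the general exception to dosing, and Section 11.1 skips any dose that severe emesis prevents. Dosing is weekly and the mean half-life is about 8 hours (Section 3.1), so many short events will end before the next dose. The safety analysis is single-arm and descriptive, and event grades are reported whichever rule is used.

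These points stand and limit the weight of the concern. They do not settle it. Section 11.1.2 is headed as the criteria for interruption and names nausea and emesis itself, while Section 11.6.5 calls Table 12 guidance, so neither is clearly the governing text. The skipped-dose rule does not cover severe nausea that still lets the patient swallow the capsules.

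It can also be said that the exceptions in 11.3 are simply incomplete, since Table 17 suggests corticosteroids for pneumonitis although 11.3 names only rash. That may be so, but no text extends the exceptions to antiemetic use.

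A reader might infer more than the documents support:

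- **That the plan directs 30 mg dosing through severe emesis.** It does not: the waiver is permissive and says nothing about dose level. A 30 mg next dose is inferred from the absence of any interruption.
- **That every event over 72 hours produces a 30-versus-20 mg conflict.** This holds only under the first reading in Step 4.
- **That the steroid ban creates the disagreement with Table 12.** For events up to 72 hours the table's hold has no prophylaxis condition, so it would differ from the waiver in any patient without prophylaxis, even if steroids were allowed. The ban widens the overlap to nearly all compliant patients.

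**Conclusion.** The concern holds in a limited form. The waiver in 11.1.2 depends on a regimen that 11.3 prohibits, so in compliant patients it covers essentially every grade ≥3 nausea or emesis event. Table 12 directs a hold for events up to 72 hours, and for longer ones where its *optimal therapy* condition can be met. No text ranks the two. The firm conflict is over whether that hold is mandatory.

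The dose-level difference for events over 72 hours is conditional on reading *optimal therapy* as the best therapy 11.3 permits. The 10 to 210 mg losses illustrate that reading; they are not expected effects. The larger ones assume up to three weeks without recovery and a comparison patient who takes every 30 mg dose, some of which Section 11.1 might skip.

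The number of patients affected is unknown, because the documents give no rate of grade ≥3 nausea or vomiting. The Ki67 analysis, sample size and power are not affected. This is a safety rule that misfires as written. It is worth correcting, but it does not threaten the trial's validity.

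**What to change.** 1. In Section 11.1.2, either delete the nausea/emesis exception or redefine optimal antiemetic prophylaxis as a regimen that 11.3 permits, for example a 5-HT3 antagonist with or without another non-steroid antiemetic.
2. State in 11.1.2 that Table 12 governs holding, resumption and dose level for grade ≥3 nausea or vomiting. Once this is said the exception has little left to do, so deletion is the cleaner choice.
3. In Table 12, define *optimal therapy* in the same 11.3-compatible terms. A sentence on events over 72 hours without such therapy would close the remaining gap.

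Section 11.3 can stay as it is. Hyperglycemia is a known TAK-228 toxicity (Section 4.1.1) and recent systemic steroid use is already an exclusion, so adding a steroid exception is the less attractive route.

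The cost is a short wording amendment to 11.1.2 and Table 12, and possibly a few more recorded holds or reductions. Visits, sample size and analysis do not change. Grade 3 fatigue has a similar overlap, between 11.1.2 and Table 15, and could be settled in the same amendment.

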**TABLE 7 TAK-228 DOSE MODIFICATIONS**

Dose Level	TAK-228 Dose	TAK-228 Number of Capsules and Strength
0	30 mg p.o. QW	Six 5 mg capsules
-1	20 mg p.o. QW	Four 5 mg capsules
-2	15 mg p.o. QW	Three 5 mg capsules
-3	10 mg p.o. QW	Two 5 mg capsules

For patients who are unable to tolerate the protocol-specified dosing schedule, dose reductions or interruptions are permitted to manage drug-related toxicities. Patients whose treatment is interrupted or permanently discontinued due to an AE including abnormal laboratory value must be followed at least once a week for 4 weeks and subsequently at 4-week intervals until resolution or stabilization of the event, whichever comes first. Dose interruptions should be reported on the appropriate Dosage Administration case report form (CRF). The maximum time allowed for toxicity-related treatment interruption is 21 days (3 weeks) from the intended dosing day. If treatment interruption is >3 weeks or more than 3 dose reductions are required, the patient must be discontinued from the study treatment. However, they will need to complete the EOT visit within 30 to 40 days after the last dose of TAK-228, and the patient will continue to be followed for toxicity.

## **11.2 Recommended Dose Modifications for Tamoxifen Treatment-Associated Toxicity**

There are no recommendations for tamoxifen dose modifications.

## **11.3 Excluded Concomitant Medications and Procedures and Potential DDIs**

The following medications and procedures are prohibited during the study:

- Other investigational agents including mTOR, PI3K, and AKT inhibitors
- Other anticancer therapies including chemotherapy, immunotherapy, radioimmunotherapy, targeted agents, radiation, and surgery (palliative radiation and surgery for preexisting lesions is allowed during the study)
- Systemic corticosteroids (either IV or oral steroids, excluding inhalers), unless necessary for the treatment of TAK-228-related rash.
- Antiepileptic drugs for patients with treated brain metastasis
- Concomitant administration of any PPI (e.g., omeprazole, esomeprazole, pantoprazole, lansoprazole, and rabeprazole) is not permitted during the study. Patients receiving PPI therapy before enrollment must stop using the PPI for 7 days before their first dose of study drugs.

## **11.4 Permitted Concomitant Medications and Procedures**

- Histamine H2 receptor antagonists (e.g., ranitidine, famotidine, and nizatidine) may be allowed, if needed, provided they are not taken within 12 hours before and within 6 hours after administration of the study drugs. Patients receiving histamine H2 receptor antagonists before enrollment must stop using these medications for at least 24 hours before their first dose of the study drugs. Cimetidine, a moderate CYP1A2 inhibitor, is not recommended as a first choice H2 receptor antagonist.

- Neutralizing antacid preparations (acid neutralizers) and calcium supplements are permitted except from 2 hours before until 2 hours after TAK-228 administration. Some anti-gas preparations may also have antacid properties and should also not be permitted from 4 hours before until 2 hours after study drug administration.
- Strong CYP1A2 inhibitors and CYP inducers should be administered with caution, at the discretion of the investigator (see Appendix E). Alternative treatments, if available, should be considered..

### 11.5 Precautions and Restrictions

No dietary restrictions will be imposed on study patients other than the daily fasting glucose test. Patients are required to fast for glucose monitoring and refrain from eating or drinking for 2 hours before and 1 hour after each dose.

Patients who show evidence of hyperglycemia during the study should be encouraged to follow a low carbohydrate diet.

Patients should be encouraged to drink at least 20 ounces of fluids a day, especially on days requiring fasting.

#### Pregnancy

The effects of TAK-228 on human pregnancy and the development of the embryo or fetus are not known. Therefore, female and male patients participating in this study should avoid becoming pregnant or impregnating a partner, respectively.

Women of childbearing potential and men should use effective methods of contraception during and through 90 and 120 days after the last dose of study drug, respectively, as specified below.

Women must meet 1 of the following:

- Postmenopausal for at least 1 year before the screening visit, OR
- Surgically sterile, OR
- If they are of childbearing potential, agree to practice 1 highly effective method of contraception and 1 additional (barrier) method, at the same time from the time of ICF signing up to and including 90 days (or longer, as mandated by local labeling [e.g., United Surgical Partners International, summary of product characteristics, etc.]) after the last dose of the study drugs, OR
- Agree to practice true abstinence, when this is in line with the preferred and usual lifestyle of the patient. (Periodic abstinence [e.g., calendar, ovulation, symptothermal, and postovulation methods] and withdrawal, spermicides only, and lactational amenorrhea are not acceptable methods of contraception. Female and male condoms should not be used together.)

Males, even if surgically sterilized (i.e., status postvasectomy), must:

- Agree to practice highly effective barrier contraception during the entire study treatment period and through 120 days after the last dose of study drug, OR
- Agree to practice true abstinence, when this is in line with the preferred and usual lifestyle of the patient. (Periodic abstinence [eg, calendar, ovulation, symptothermal, postovulation methods for the female partner], withdrawal, spermicides only, and lactational amenorrhea are not acceptable methods of contraception. Female and male condoms should not be used together.)
- Agree not to donate sperm during the course of this study or 120 days after receiving their last dose of study drug.

## 11.6 Management of Clinical Events

### 11.6.1 Management of Hyperglycemia

Based on the TAK-228 clinical trials, most hyperglycemia episodes occurred within the first 60 days after initiation of treatment with TAK-228 and have been grade 1 or 2 and have responded quickly to oral metformin. Hyperglycemia has not been dose-limiting since instituting a standard regimen for early treatment of hyperglycemia.

All patients who develop hyperglycemia during the study should have their glucose closely monitored by study staff. The investigator may choose either to continue close monitoring of patients who develop grade 1 hyperglycemia ( $FSG > ULN \leq 160$  mg/dL) or, alternatively, consider initiating treatment with an oral hypoglycemic agent, such as metformin. All patients with grade  $\geq 2$  hyperglycemia ( $FSG > 160$  mg/dL) must be treated aggressively with oral hypoglycemic agents and/or insulin as clinically indicated while continuing on TAK-228. The investigator should consult an endocrinologist, if needed, to aid in optimizing the patient's hyperglycemia treatment plan.

It is recommended that patients be treated initially with a fast-acting insulin sensitizer, such as metformin, at 500 mg p.o. QD and titrate up to a maximum of 1000 mg p.o. twice daily as needed. Concurrent administration of dipeptidyl peptidase-4 inhibitors (e.g., sitagliptin or vildagliptin) and/or insulin should also be considered. Oral sulfonylureas (e.g., glipizide or glyburide) should be used with caution due to the higher hypoglycemia risk. The dose of oral hypoglycemic agents should be adjusted in patients with renal insufficiency. Hyperglycemic patients should also be encouraged to follow a low carbohydrate diet.

If any fasting serum glucose reading performed at the site indicates hyperglycemia ( $> ULN$  or  $\geq 110$  mg/dL), the study staff should first ascertain that the patient was fasting at the time of the blood draw (i.e., nothing by mouth for at least 8 hours prior to blood being obtained).

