#### 11.1.1 Dose Modification Guidelines

TAK-228 should be administered, unless the patient has a grade 3 or greater TAK-228-related event. Guidelines for dose interruption and dose reduction are described below.

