### In-Home Daily Fasting Glucose Monitoring

In addition to obtaining fasting glucose levels at the clinic visits as outlined in the Schedule of Events, all patients will be given a glucometer to monitor their daily FBG levels at home. The level should be collected daily, predose on dosing days, and at approximately the same time each day.

On Cycle 1 Day 1, the patient will be provided an in-home glucometer. Patients will be trained on proper use of the glucometer and instructed to collect a daily FBG level every morning (predose on dosing days), starting on Cycle 1 Day 2. Patients will be instructed to bring the glucometer with them to each study visit so that the data collected can be reviewed and recorded in the source documents. Investigators will be responsible for reviewing the home glucose monitoring logs for hyperglycemia.

The patient will be instructed to contact the site immediately if the value is abnormal (i.e.,  $\geq 150$  mg/dL) for further instructions on the management of their hyperglycemia. Hyperglycemia observed during home glucose monitoring should be confirmed in the clinic.

If no irregularities in the fasting blood glucose level are observed during a minimum of 2 consecutive months, then the frequency of in-home fasting blood glucose testing can be reduced to a minimum frequency of once weekly, depending on the investigator's judgment and approval. Patients will continue to notify the investigator of fasting blood glucose levels that exceed 150 mg/dL and, if blood glucose levels are not well controlled, or if the patient requires either oral hypoglycemic agents or insulin to control blood glucose levels, then the frequency of in-home testing of FBG levels will be reinstated to daily.

Guidance on TAK-228 dose modification for patients with hyperglycemia is provided in Table 8 below.

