**TABLE 8 MANAGEMENT OF HYPERGLYCEMIA**

Grade	Description	Treatment	Dose Modification
1	Fasting blood sugar >ULN to 160 mg/dL	
 
Continue close monitoring of blood sugar.
 
Initiate oral hypoglycemic agent.
 
	None
2	>160 to 250 mg/dL	
 
Initiate oral hypoglycemic agent and/or insulin if not well controlled on oral agent.
 
	None
≥3	>250 mg/dL	
 
Initiate oral hypoglycemic agent and/or insulin.
 
	Hold TAK-228 until ≤grade 2. Resume TAK-228 based on timing of recovery after maximal treatment: 
 
≤1 week: resume TAK-228 at same dose and schedule.
 
>1 but ≤2 weeks: reduce TAK-228 by 1 dose level
 
>2 weeks: discontinue patient from the study.
 

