**TABLE 16 MANAGEMENT OF AST/ALT ELEVATIONS**

Grade	Description	Treatment	Dose Modification
1	>ULN to 3×ULN	None	None
2	Asymptomatic with levels 3 to 5×ULN; >3×ULN with the appearance of worsening fatigue, nausea, vomiting, right upper quadrant pain or tenderness, fever, rash, or eosinophilia.	
 
Closely monitor LFTs at least weekly or more frequently as indicated.
 
Assess patient for other causes of transaminitis (e.g., past medical history, concomitant medications).
 
	None
3	>5 to 20×ULN; >5×ULN for >2 weeks	Same as for grade 2.	Hold TAK-228 until ≤grade 1; Restart TAK-228 at the same dose. Permanently discontinue study treatment if in combination with grade 2 total bilirubin elevation when alternative causes cannot be identified (i.e., Hy's Law).
4	>20×ULN	Same as for grade 2.	Stop TAK-228 and discontinue patient from the study. Permanently discontinue study treatment if in combination with grade 2 total bilirubin elevation when alternative causes cannot be identified (i.e., Hy's Law).

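### Section 11.6.1 tells sites to keep giving TAK-228 at every hyperglycemia grade from 2 upward, against the hold above 250 mg/dL in Table 8 and the grade 3 rule in 11.1.1; 11.1.2 also disagrees with Table 16 on restart dose and with Table 8 on the recovery limit

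*Combined protocol and SAP*

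**What the plan says.** **Whether to dose.** Section 11.6.1 covers all patients at grade 2 or above, defined only as fasting serum glucose (FSG) over 160 mg/dL, and says they "must be treated aggressively with oral hypoglycemic agents and/or insulin as clinically indicated while continuing on TAK-228". Table 8 separates the grades. At grade 2 (over 160 and up to 250 mg/dL) it makes no dose change. At grade 3 or higher (over 250 mg/dL) it starts glucose-lowering treatment and adds "Hold TAK-228 until ≤grade 2". Section 11.1.1 gives the general rule: "TAK-228 should be administered, unless the patient has a grade 3 or greater TAK-228-related event". The home-monitoring text in 11.6.1 adds a pointer: "Guidance on TAK-228 dose modification for patients with hyperglycemia is provided in Table 8 below".

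**Restarting.** Section 11.1.2 withholds the drug for related toxicity of grade 3 or higher that occurs in spite of supportive care. If the event resolves to grade 1 (grade 2 for hyperglycemia or rash) or to baseline "within 3 weeks of interrupting treatment, then the patient may resume study treatment at a dose level reduced by 1 level". Several tables differ:

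- Table 8, hyperglycemia recovered within 1 week: "resume TAK-228 at same dose and schedule". Recovery in more than 1 and up to 2 weeks means one level lower. Beyond 2 weeks the patient is discontinued from the study.
- Table 12, nausea or vomiting of grade 3 or higher: "If experienced for ≤72 hours, hold TAK-228 until ≤grade 1, then resume TAK-228 without dose modification".
- Table 16, grade 3 AST/ALT after recovery to grade 1: "Restart TAK-228 at the same dose".

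The text under Table 7 caps any toxicity-related interruption at 21 days and requires discontinuation if more than 3 reductions are needed. No passage says which rule prevails when they differ.

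**The concern.** Hyperglycemia is a known toxicity of TAK-228 (Section 4.1.1). Patients measure fasting glucose before the dose on dosing days, so a value above 250 mg/dL can appear just when someone must decide whether the dose is given. At that point a mandatory sentence says continue and a table in the same section says hold.

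The other two mismatches are smaller. The restart dose decides whether a patient returns at 30 or 20 mg and whether one of the three permitted reductions is used up. The recovery limit decides whether a patient whose glucose settles in the third week leaves the study or resumes one level lower. Section 13.1.8 reports interruptions, reductions and discontinuations as safety results, so sites following different rules would blur those counts.

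**Working it through.** The plan states no figure to reproduce here. The check sets the rules side by side, case by case.

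| Case | One rule | Other rule | Result |
|---|---|---|---|
| 1. FSG above 250 mg/dL | 11.6.1: treat and continue | Table 8: treat and hold; 11.1.1: no dosing at a grade 3 related event | Contradiction |
| 2. Grade 3 AST/ALT, recovered to grade 1 within 3 weeks | Table 16: same dose | 11.1.2: one level lower | Clear mismatch |
| 3. Grade ≥3 hyperglycemia, recovered in >2 to ≤3 weeks | Table 8: discontinue | 11.1.2: resume one level lower | Clear mismatch |
| 4. The same, recovered in >1 to ≤2 weeks | Table 8: one level lower | 11.1.2: one level lower | Agree |
| 5. The same, recovered in ≤1 week | Table 8: same dose | 11.1.2: one level lower, if the event occurred in spite of supportive care | Partial mismatch |
| 6. Grade ≥3 nausea/vomiting for ≤72 hours | Table 12: same dose | 11.1.2: one level lower, if it occurred in spite of optimal prophylaxis | Partial mismatch |

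**Case 1.** The 11.6.1 sentence cannot be read as grade 2 only, because it names grade 2 and above and sets no ceiling. A treat-first, hold-later reading also fails: Table 8 starts treatment and holds together, and 11.1.1 carries no condition about supportive care. Section 4.1.1 gives almost the same treatment instruction for grade 2 and above but does not say that dosing continues. The error is therefore that one phrase, applied to grade 3 and above.

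**Case 2.** Table 16 lists only monitoring and a search for other causes, so the supportive-care condition in 11.1.2 does not separate the two rules.

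**Case 3.** Section 11.1.2 names hyperglycemia when it defines recovery, so it sets its own rule for this toxicity. An event still unresolved 2 weeks after maximal treatment has plainly persisted in spite of supportive care, so the 11.1.2 condition is met.

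**Sizes.**

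- Restart dose, level 0 to level −1 in Table 7: (30 − 20) / 30 = 33.3% lower per week. A restart under 11.1.2 uses 1 of the 3 allowed reductions; a same-dose restart uses 0.
- Recovery window: 11.1.2 counts 21 days from interruption. Table 8 counts 14 days after maximal treatment. If maximal treatment starts d days after the hold, the window of disagreement is 21 − (14 + d) = 7 − d days. The documents do not give d. Taking d from 0 to 7 as an assumption, the window runs from 7 days down to 0.

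**The case against.** The strongest reply is that the intent is easy to find. Section 11.1.1, 11.1.2 and Table 8 all stop dosing at grade 3, the home-monitoring text sends the reader to Table 8, and Section 4.1.1 omits the phrase about continuing. Patients call the site at 150 mg/dL or more, so dosing unnoticed above 250 mg/dL is unlikely. All of this stands as evidence of intent. It does not correct the sentence: the pointer offers guidance, 11.6.1 is mandatory, and nothing ranks one above the other. A reader might go further and infer that the protocol means to dose through severe hyperglycemia. The documents do not support that, for the same reasons.

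A second reply is that toxicity-specific tables commonly refine a general rule, and that 11.1.2 only says a patient may resume. The first part is fair, and an explicit precedence sentence would settle it. The second does not help: the permission concerns whether to resume, and the dose that follows is fixed at one level lower.

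Two stronger readings should be set aside.

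- A reader might count three tables in full conflict with 11.1.2 on restart dose. Only Table 16 conflicts clearly. The 1-week branch of Table 8 can be read as an event that responded to treatment, outside the 11.1.2 condition. The longer-lasting branch of Table 12 matches 11.1.2. Its 72-hour branch conflicts only for a short event in spite of optimal prophylaxis, because 11.1.2 exempts nausea and vomiting without such prophylaxis from interruption.
- A reader might also set the 2-week limit in Table 8 against the 21-day cap under Table 7. That cap is a maximum, and a stricter limit fits beneath it. The disagreement is with 11.1.2 alone.

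**Conclusion.** Section 11.6.1 is wrong as written for grade 3 and above and should be corrected. This is one contradiction on whether to dose, in a safety instruction, even though Table 8 is probably intended. Two clear secondary mismatches remain: the restart dose for grade 3 AST/ALT (33.3% of the weekly dose at the first step), and hyperglycemia that recovers in the third week (a window of 0 to 7 days, depending on when maximal treatment starts). The same-dose branches of Tables 8 and 12 are partial mismatches only.

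Practical exposure is limited. Dosing is weekly, the mean half-life is about 8 hours (Section 3.1), entry requires FSG of 130 mg/dL or less (Section 10.1), and most past episodes were grade 1 or 2 (Section 11.6.1). The documents give no frequency for hyperglycemia of grade 3 or higher, so the number of patients affected cannot be estimated. A reader might infer damage to the Ki67 result, but neither the power calculation nor the primary test uses any of these rules.

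**What to change.** Make two wording changes.

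1. **Section 11.6.1.** Limit the sentence that ends "must be treated aggressively with oral hypoglycemic agents and/or insulin as clinically indicated while continuing on TAK-228" to grade 2, with FSG above 160 and up to 250 mg/dL. Then add: *For grade 3 or higher (above 250 mg/dL), start the same treatment and hold TAK-228 per Table 8.*

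2. **Section 11.1.2.** Add: *Except for the exemptions listed in this section, where a table in Section 11.6 gives a hold, restart-dose or discontinuation rule, that table governs. The 21-day maximum interruption, the limit of 3 dose reductions and the follow-up requirements below Table 7 apply to all toxicities unless a table is stricter.*

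The opening clause of the second change is needed. Without it, Table 15 would override the current exemption for grade 3 fatigue and impose a hold and a reduction, which is a dosing change and not a clarification. The second sentence keeps the 21-day cap for tables that state no maximum hold (Tables 9, 10, 12, 14 and 15, and grade 3 in Tables 16 and 17) and leaves the 2-week limit in Table 8 in force.

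The cost is a protocol amendment in two places. It adds no patients, visits or procedures, and the existing exemptions stay as they are.
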